9.4 Analysis Plan

TOX events will be reported with a 95% credible interval assuming a non-informative prior of beta (1,1). Specific events will also be summarized. Then all adverse events and surgical complications will be reported overall by grade, attribution, and treatment period (cycle 1, cycle 2, between the end of cycle 2 and actual surgery, 30 days following surgery). Demographic and baseline laboratory results will be summarized using descriptive and graphical statistics. Changes in markers between biopsy and surgical resection will be compared with a paired t-test or non-parametric alternative as indicated for continuous measures, and with McNemar's test for binary or ordinal measures. The numbers of patients with sufficient samples for laboratory analysis will be used to plan the numbers of patients needed for enough evaluable samples future trials. Similarly this experience will guide planning for the numbers and types of markers that can be reasonably assessed from surgical specimens in this patient population after 'window of opportunity' pembrolizumab treatment.

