2.1.2 Correlative Studies

All participants will be required to participate in the collection of blood and tissue sample for banking and future research studies. Up to 60 mL of blood will be collected at each of the following time points: baseline or pre-treatment, after the first cycle of treatment, after the second cycle of treatment and post cystectomy.

We will also collect archival tissue from a newly obtained core or excisional biopsy of a tumor lesion. Newly-obtained is defined as a specimen obtained up to 6 weeks (42 days) prior to initiation of treatment on week 1. Subjects for whom newly-obtained samples cannot be provided (e.g. inaccessible or subject safety concern) may collect tissue from a previously archived specimen. Additionally, archival tissue from the surgical specimen at the time of cystectomy will also be collected.

Laboratory assays will be used to explore our hypothesis that there will be markers of immune activation/biologic response in the tumors of patients treated with pembrolizumab as compared to control untreated tumor samples from similar patients or the same patient (if tissue is available). This will include, but not be limited to, studying signals of anti-cancer

immunological activity by evaluating the frequency of CD4 and CD8 T cells in tumor tissues (pre and post-therapy or untreated and treated cohorts). We will also evaluate tissue for signals of biomarker activity by evaluating surgical specimens for established and not-so-established markers of response to pembrolizumab (e.g. TILs, PD-1 and PD-L1 levels) compared to pre-treatment biopsy samples. Immune monitoring as a component of internal discovery studies will include but not limited to evaluation of CD4 and CD8 T cells in peripheral blood and available tumor samples as previously published[1-4].

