9.1 STATISTICAL CONSIDERATIONS

The purpose of this study is to assess the safety of treatment with pembrolizumab (two cycles) in the ‘window of opportunity’ setting for bladder cancer patients who are scheduled to undergo radical cystectomy. Secondary endpoints for efficacy and biomarker activity will be described and used to design future studies.

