9.1.3 Lymphocytic infiltration pre and post treatment

Pre and post treatment tumor specimens will be formalin-fixed and paraffin-embedded on slides and stained with H&E and evaluated by the collaborator pathologist for the presence/absence of lymphocytes within the tumor tissue.

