9.1.4 Residual tumor

This will be reported as whether there is any residual tumor in the surgical specimen (present /absent) as well as area of the surgical specimen comprised of residual tumor.

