9.1.5 Biomarker activity

Immunological markers include CD4 and CD8 T cells and biomarker activity includes TILs, PD-1 and PD-L1 levels. These will be measured from the biopsy samples and surgical specimens.

9.1.6 Tumor Yield.

The amount of residual tumor available for analysis and the numbers of patients with assessable samples will be recorded.

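### Minor: section 9.4 assigns McNemar's test to ordinal marker changes, but that test needs a paired 2x2 table, so a marker with three or more ordered levels has no workable test as written

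*Combined protocol and SAP*

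**What the plan says.** Section 9.4 (Analysis Plan) sorts marker changes between biopsy and resection by data type. Continuous markers get a "paired t-test or non-parametric alternative as indicated for continuous measures". All others are compared "with McNemar's test for binary or ordinal measures". The documents give no cut for reducing an ordinal marker to two levels, and name neither a k x k extension of McNemar's test nor a paired ordinal test.

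The endpoint definitions say little about scale:

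- Section 9.1.3: lymphocytic infiltration is read as "presence/absence of lymphocytes within the tumor tissue", which is binary.
- Section 9.1.4: residual tumor is "whether there is any residual tumor in the surgical specimen", plus an area. Both are defined on the surgical specimen.
- Section 9.1.5: "Immunological markers include CD4 and CD8 T cells and biomarker activity includes TILs, PD-1 and PD-L1 levels". No scale, number of categories or threshold follows. Section 2.1.2 describes "evaluating the frequency of CD4 and CD8 T cells in tumor tissues", which suggests a continuous measure for those two.
- Section 2.1.2 also assigns tumors to basal and luminal subtypes, which is two classes as written.

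On the role of these endpoints, section 9.1 says: "Secondary endpoints for efficacy and biomarker activity will be described and used to design future studies". The cohort is 20 patients (section 9.2, Sample Size Considerations). Section 9.1.6 adds that "the numbers of patients with assessable samples will be recorded", so fewer than 20 complete pairs is a foreseen outcome. Section 2.1.7 likewise allows for patients whose own pre-treatment tissue is not available.

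**The concern.** McNemar's test uses two counts: the pairs that move from negative to positive and the pairs that move from positive to negative. With three or more ordered levels there is no single such pair of counts. An analyst following 9.4 literally must first choose a cut, or substitute another test under the same name. Either step goes beyond what the plan specifies, and both can change the answer.

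The loss is in ordering. A patient who moves from level 1 to level 2 counts as changed under one cut and unchanged under another. With at most 20 pairs, few changes will fall across any one cut. The choice of cut or extension would also be open when the data are in hand. These comparisons are meant to inform the design of later studies, so a graded marker could look unaffected, or affected, because of an analysis choice the plan did not make.

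**Working it through.** There is no stated figure to reproduce: the documents give no alpha, power or effect size for the marker tests. The check is whether the test fits the data type, followed by two illustrations. All inputs to the illustrations are assumed except the 20 pairs, which is the cohort size and so the maximum.

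**Fit of test to scale.** With b pairs moving up across a cut and c moving down, McNemar's test refers b to Binomial(b + c, 1/2) (exact form), or (b - c)^2/(b + c) to chi-square on 1 df. It is right for infiltration (present/absent) and for a two-class subtype. It is undefined for a 3x3 or larger table until a cut is chosen.

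**One invented data set, 20 pairs, levels 0/1/2.** Four pairs move 0 to 1, five move 1 to 2, one moves 1 to 0, and ten do not move.

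| Reading of 9.4 | Calculation | p |
|---|---|---|
| McNemar, cut at level 1 or above: 4 up, 1 down | exact: 2 x (1 + 5)/2^5 | 0.375 |
| | chi-square: 3^2/5 = 1.8, 1 df | 0.180 |
| McNemar, cut at level 2: 5 up, 0 down | exact: 2 x 1/2^5 | 0.0625 |
| | chi-square: 5^2/5 = 5.0, 1 df | 0.025 |
| Bowker symmetry | 1.8 + 5.0 = 6.8, 3 df | 0.079 |
| Stuart-Maxwell | 6.8, 2 df | 0.033 |
| Exact sign test: 9 up, 1 down | 2 x (1 + 10)/2^10 | 0.021 |

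Every change here is one level, so all absolute differences tie and the exact signed-rank test equals the sign test (0.021). Its normal approximation gives 0.011: z = (9 - 1)/sqrt(10) = 2.53. The same 20 patients thus give p-values from 0.025 to 0.375 under readings that all go by the name McNemar's test. Bowker's test, if that was meant, also ignores the order of the levels. The exact form needs at least six changes across the cut, all one way, to reach p < 0.05 (6 of 6: 2/2^6 = 0.031; 5 of 5: 0.0625).

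**Simulated power.** Assumed: bivariate normal latent scores with correlation 0.5, cut at -0.6745, 0 and 0.6745 into four levels, a shift of 0.75 SD, rejection at two-sided p <= 0.05. Signed-rank is the exact conditional test on midranks with zeros dropped; chi-square McNemar is uncorrected. There were 100,000 data sets per cell, and a separate run of 40,000 agreed within simulation error.

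| Pairs | Exact signed-rank | Exact sign | Chi-square McNemar, by cut | Exact McNemar, by cut |
|---|---|---|---|---|
| 20 | 73% | 62% | 37%, 54%, 55% | 13%, 38%, 39% |
| 15 | 55% | 46% | 25%, 43%, 44% | 5%, 21%, 23% |
| 10 | 28% | 23% | 10%, 28%, 29% | 1%, 5%, 6% |

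**Rejection when nothing has changed, 20 pairs.** Signed-rank 3.6%, sign 2.4%, chi-square McNemar 4.7-5.0%, exact McNemar 1.0-1.6%. Part of the gap between signed-rank and exact McNemar is therefore the latter's conservatism. The 20-pair gap to chi-square McNemar is not, because chi-square McNemar rejects more often than signed-rank under no change.

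**Picking the best of three cuts after seeing the data.** Under no change, chi-square McNemar rejects in 13%, 13% and 8% of data sets at 20, 15 and 10 pairs. Exact McNemar rejects in 3%, 2% and 0.4%.

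**The case against.** The strongest reply is that nothing in the plan is shown to trigger the problem. Infiltration and subtype are two-class. Residual tumor is defined on the surgical specimen. CD4 and CD8 are frequencies, and PD-1 and PD-L1 levels can be read as continuous, in which case the t-test or its alternative covers them. The only sign of an ordinal marker is the word in 9.4. This stands as a limit on consequence. It does not rescue the rule, because 9.4 itself provides for ordinal measures and gives them a test that cannot be applied as stated.

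Second, no decision rests on a marker p-value. The planning uses that 9.4 spells out are counts of evaluable samples and the markers that can reasonably be assessed. That also stands, and it is why the point is minor.

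Third, the power figures rest on invented inputs and there is no target in the plan to miss. At 10 pairs signed-rank (28%) does no better than chi-square McNemar at its two better cuts (28% and 29%). Both statements are correct. The figures show direction, not the expected performance of this trial.

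A reader might also infer that choosing a cut late inflates false positives whichever form of the test is used. In these scenarios it does so only for chi-square McNemar; best-of-three with the exact form stays below 5%. Section 9.4 does not say which form is meant.

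**Conclusion.** The rule in 9.4 is wrong as written for ordinal measures, and the defect is minor. That conclusion needs no simulation: McNemar's test requires two categories, and the documents supply no cut, extension or paired ordinal test. Whether it affects any result depends on a marker being scored on three or more ordered levels, which 9.4 allows for but the endpoint sections do not establish. The size, under the stated assumptions, is about 73% (signed-rank) or 62% (sign) against 37-55% (chi-square McNemar) at 20 pairs. The advantage over McNemar's better cuts disappears at 10 pairs.

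Three stronger readings are not supported. The primary safety analysis, its monitoring rule and the sample size are not touched, because none of them uses a marker test. The documents do not show that any particular marker will be analysed wrongly. Nor do they show a need to replace McNemar's test with its exact form for binary markers: chi-square McNemar holds 4.7-5.0% at 20 pairs in the illustration, and the exact form would cost power.

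**What to change.** In section 9.4, replace the categorical half of the sentence with: *McNemar's test for binary measures and the Wilcoxon signed-rank test (exact, allowing for ties) for ordinal measures, or the exact sign test where differences between levels cannot be taken as comparable.*

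The cost is one phrase, with no new data or patients. The trade-off is that the signed-rank test treats steps between levels as comparable. The sign test avoids this by using only rises and falls, at some loss of power (62% against 73% at 20 pairs in the illustration). If every marker turns out to be binary or continuous, deleting the reference to ordinal measures would do equally well. A scale and cut for each marker would be useful detail, but the marker list in section 2.1.2 is open-ended and this correction does not depend on it.

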10.0 INVESTIGATIONAL PRODUCT

The investigator shall take responsibility for and shall take all steps to maintain appropriate records and ensure appropriate supply, storage, handling, distribution and usage of investigational product in accordance with the protocol and any applicable laws and regulations.

Clinical supplies must be stored in a secure, limited-access location under the storage conditions specified on the label.

Receipt and dispensing of trial medication must be recorded by an authorized person at the trial site.

Clinical supplies may not be used for any purpose other than that stated in the protocol.

Clinical supplies will be affixed with a clinical label in accordance with regulatory requirements.

The investigator is responsible for keeping accurate records of the clinical supplies received from Merck or designee, the amount dispensed to and returned by the subjects and the amount remaining at the conclusion of the trial.

Upon completion or termination of the study, all unused and/or partially used investigational product will be destroyed at the site per institutional policy. It is the Investigator's responsibility to arrange for disposal of all empty containers, provided that procedures for proper disposal have been established according to applicable federal, state, local and institutional guidelines and procedures, and provided that appropriate records of disposal are kept.

11.1 ADMINISTRATIVE AND REGULATORY DETAILS

11.2 Confidentiality

All pathology specimens, evaluation forms, reports and other records will be identified in a manner designed to maintain patient confidentiality. All records will be kept in a secure storage area with limited access. No patient identifiers will be used when analyzing the data or reporting the results.

11.3 Compliance with Financial Disclosure Requirements

Before the start of the study, the investigator and each sub-investigator will disclose any proprietary or financial interests. The investigator agrees to update this information during the study or within one year of its completion.

11.4 Compliance with Law, Audit and Debarment

The institution represents and warrants that neither it, the Principal Investigator, nor any of the Institution's employees performing the Study is (a) under investigation by the Food and Drug Administration ("FDA") or equivalent authority in connection with an action to debar, disqualify, or prohibit such person or entity from participating in human research or (b) presently debarred, disqualified or prohibited pursuant to 21 U.S.C. §

335(a) and 335(b) or any other applicable law or by any regulatory authority or government entity.

11.5 Compliance with Trial Registration and Results Posting Requirements

Under the terms of the Food and Drug Administration Modernization Act (FDAMA) and the Food and Drug Administration Amendments Act (FDAAA), the Sponsor of the trial is solely responsible for determining whether the trial and its results are subject to the requirements for submission to the Clinical Trials Data Bank, <http://www.clinicaltrials.gov>. Information posted will allow subjects to identify potentially appropriate trials for their disease conditions and pursue participation by calling a central contact number for further information on appropriate trial locations and trial site contact information.

12.1 APPENDICES

12.2 ECOG Performance Status

Grade	Description
0	Normal activity. Fully active, able to carry on all pre-disease performance without restriction.
1	Symptoms, but ambulatory. Restricted in physically strenuous activity, but ambulatory and able to carry out work of a light or sedentary nature (e.g., light housework, office work).
2	In bed <50% of the time. Ambulatory and capable of all self-care, but unable to carry out any work activities. Up and about more than 50% of waking hours.
3	In bed >50% of the time. Capable of only limited self-care, confined to bed or chair more than 50% of waking hours.
4	100% bedridden. Completely disabled. Cannot carry on any self-care. Totally confined to bed or chair.
5	Dead.

* As published in Am. J. Clin. Oncol.: Oken, M.M., Creech, R.H., Tormey, D.C., Horton, J., Davis, T.E., McFadden, E.T., Carbone, P.P.: Toxicity And Response Criteria Of

The Eastern Cooperative Oncology Group. Am J Clin Oncol 5:649-655, 1982. The Eastern Cooperative Oncology Group, Robert Comis M.D., Group Chair.

